Our primary endpoint is the number of emergency hospital admissions per patient, which is a commonly used endpoint in evaluative studies of integrated care. Our secondary endpoint is the number of hospital bed days per patient over twelve months, as this reflects changes to the length of stay in hospital as well as the number of admissions.

Other endpoints will be the notional cost of care per patient, including primary and secondary care cost and other indicators listed above.

Sample size calculation

Our sample size will be sufficient to identify a 15% change in emergency admissions between the enrolled patients and the matched control group. Our sample size calculation was performed in SAS with 90% power and a two-sided p-value of 0.05. We assumed an average number of emergency admissions per patient per year of 0.6 with a standard deviation of 1.4. These assumptions are based on a previous study with a similar population base (Steventon, Bardsley, Billings, Dixon, et al. 2012).

The sample size calculation indicate that in order to identify a 15% change in emergency admission a sample size of 10,174 is required in case of a balanced sample (1 control per enrolled patient), or 11,445 in case of a sample with two controls per enrolled patient. In comparison, we estimate that our study will include at least 6,360 integrated care patients. In a matched control design with one control patient per integrated care patient, the total sample size would therefore be 12,720 patients. If there were two control patients per integrated care patient, the total sample size would be higher, at 19,080.

Control group

In the absence of a randomised controlled trial, we will compare the outcomes of the integrated care cohort with a retrospectively matched control group. In other words, line-level routine, patient information will be used to characterise the integrated care patients as well as possible, and then select, for every patient, matched controls that were not enrolled onto the programme but had similar observed characteristics to the enrolled patient. These matched patients will form the control group for the evaluation of the programme.

Control patients will be registered with a general practice in the WELC area, and will not have been enrolled onto the integrated care pathway at any point before the end of our follow-up period.

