Preliminary analysis of aggregated data from the WELC Integrated Care Programme (using the Data Cube) suggests that the pool of potential matches is sufficiently large to select matched controls within cluster (*i.e.*, geographically clustered GPs) and within the same risk-band (top 0.5%, 0.5-5%, or 5-20%). This is because enrolment rates at cluster level vary between 17% and 38%, and enrolment rates for the different risk-bands are 50%, 24% and 2%, respectively.

Matching will be done to optimise the similarity of integrated care and matched control groups with respect to variables that are likely to be predictive of the endpoints. These variables will include:

predictive risk score; age; gender; ethnicity; prior primary and secondary care utilisation; a measure of socioeconomic deprivation (the Index of Multiple Deprivation, attributed to the Lower Super Output Area of residence); existing diagnoses of health care conditions; and numbers of prescription medications. Many of these variables feature in the Combined Predictive Model (Wennberg et al. 2006), but are included in our matching algorithm so that the groups will be similar in terms of these more detailed variables as well as the overall risk score.

To increase the number of potential controls available for the analysis, we will assign each potential control up to 12 index dates, one for each month from January 2014 to December 2014, assuming that the patient is alive at each of these time points. Baseline variables (*e.g.*, age and prior primary and secondary care utilisation) will then be calculated at each of these index dates, and each control patient will provide the matching algorithm with up to twelve observations.

Matched control observations will be selected using the genetic matching algorithm, which is a computer-intensive search procedure that produces more closely balanced groups than traditional approaches such as nearest neighbour matching on the propensity score (Sekhon & Grieve 2012). Balance will be assessed using the standardised difference, which is defined as the difference in means as a proportion of the pooled standard deviation (Austin 2009). Although the standardised difference would ideally be minimised without limit, a threshold of 10% has been used to describe meaningful difference (Normand et al. 2001). We will adjust the parameters in the genetic matching algorithm until we obtain standardised differences below these thresholds.

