The matching will be conducted with replacement, meaning that a patient might be used as the control for multiple integrated care patients. Our preference is to select two control observations per patient, as this would increase the precision of our estimates of the effect of the integrated care pathway on patient outcomes (*i.e.*, reduce the width of our confidence intervals, meaning we can be more sure about the effect size). However, if it is not possible to obtain adequate balance when selecting two controls per patient, we will rerun the matching algorithm when selecting one control per patient.

Statistical method

After adequate balance has been obtained, we will estimate the effect of the integrated care pathway on patient outcomes by fitting regression models to the data. These models will adjust for residual differences remaining between the groups in the baseline variables after matching. We will include all patients in these analyses, even if they died or moved away from the WELC area during the 12-month follow-up period.

For our primary endpoint, number of emergency hospital admissions, use of Poisson regression seems appropriate, but depending on the empirical distribution of this endpoint, alternative distributions will be considered (*e.g.*, negative binomial). We assume that ordinary least squares (linear) regression will be used

for our secondary endpoint, the number of hospital bed days. On receipt of the line-level data, we will test the suitability of these assumptions, and consider alternative distributions if appropriate. We will follow a similar procedure for other endpoints making sure that assumptions on distributions are appropriate.

Subgroup analysis

The main analysis will be pooled across all three CCGs and across all risk bands, as this approach is necessary to ensure adequate sample size. However, we will also examine whether there is evidence that the integrated care pathway affected the outcomes of certain subgroups of patients more or less than average. Specifically, we will examine subgroups defined by CCG (Newham, Tower Hamlets, and Waltham Forest) and risk band (top 0.5%, 0.5-5%, and 5-20%). We will also distinguish between patients with and without a recorded mental health condition.

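### The sample size counts control observations as independent patients, although the matching rules let one person serve as a control many times

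*Protocol*

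**What the plan says.** Three parts of the protocol bear on this.

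- **Control group.** Potential controls receive one index date per month of 2014 while alive, so that "each control patient will provide the matching algorithm with up to twelve observations". Then: "The matching will be conducted with replacement, meaning that a patient might be used as the control for multiple integrated care patients". Two control observations per enrolled patient are preferred because they are expected to narrow the confidence intervals; one is the fallback if balance is poor. Matching within geographic cluster and risk band is judged feasible, and "enrolment rates for the different risk-bands are 50%, 24% and 2%, respectively" for the top 0.5%, 0.5-5% and 5-20% bands.
- **Sample size calculation.** "Our sample size calculation was performed in SAS with 90% power and a two-sided p-value of 0.05". The inputs are: "We assumed an average number of emergency admissions per patient per year of 0.6 with a standard deviation of 1.4". The required totals are 10,174 (1:1) and 11,445 (2:1). Against these the section sets at least 6,360 enrolled patients: "In a matched control design with one control patient per integrated care patient, the total sample size would therefore be 12,720 patients". The 2:1 total is given as 19,080.
- **Statistical method.** After matching, "we will estimate the effect of the integrated care pathway on patient outcomes by fitting regression models to the data". Poisson (or negative binomial) regression is named for admissions and ordinary least squares for bed days, both provisionally. No variance method is stated.

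**The concern.** The unit being matched is a person-month, drawn with replacement. The unit in the sample size is an independent patient. They coincide only if no person is selected twice, and nothing in the matching rules secures that. One person can be the control for many enrolled patients, and can also fill both control slots of a single enrolled patient at neighbouring months, when 11/12 of a 12-month follow-up is shared.

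Two statements in the protocol depend on the missing independence: the comparison of 12,720 and 19,080 with the required totals, and the reason given for preferring a second control. A third consequence depends on the analysis. If reuse is not carried into the variance, confidence intervals on the primary endpoint will be too narrow.

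**Working it through.** **1. Reproducing the stated requirement.** Inputs from the Sample size calculation section: difference 0.15 × 0.6 = 0.09, SD 1.4, two-sided 0.05, power 90%.

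- Normal formula, per arm at 1:1: 2 × 1.4² × (1.960 + 1.282)² / 0.09² = 5,086, total 10,172.
- Noncentral t: 2 × 5,087 = **10,174** at 1:1 and 3 × 3,815 = **11,445** at 2:1, both exactly as stated.

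No design effect is needed to reach either figure, so every control is taken as a distinct, independent person.

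**2. Effect of reuse.** Let *w* be the number of times a control person is used, and D = Σw² / Σw the control-side design effect, treating repeat uses of one person as fully correlated. With n enrolled and k controls each:

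- SE = 1.4 × √(1/n + D/(kn)), and power = Φ(0.09/SE − 1.96).
- If reuse is ignored, the true SE exceeds the reported one by R = √[(1 + D/k)/(1 + 1/k)], and the type I error is 2[1 − Φ(1.96/R)].

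With n = 6,360:

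| D (assumed) | Power 1:1 | Power 2:1 | Type I 1:1, reuse ignored | Type I 2:1, reuse ignored |
|---|---|---|---|---|
| 1 | 95.2% | 98.7% | 5% | 5% |
| 1.5 | 90.0% | 97.2% | 8.0% | 7.0% |
| 2 | 84.1% | 95.2% | 11.0% | 9.0% |
| 2.5 | 78.2% | 92.8% | 13.8% | 11.0% |
| 3 | 72.7% | 90.0% | 16.6% | 12.9% |

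The type I columns isolate reuse: they take the outcome SD of 1.4 as correctly estimated, so any overdispersion left by a plain Poisson model would come on top.

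For 90% power with 6,360 enrolled, about 4,236 effective controls are needed. The limits are therefore D = 6,360/4,236 = 1.50 at 1:1 and 12,720/4,236 = 3.00 at 2:1.

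**3. What D might be.** Enrolment of 50%, 24% and 2% leaves r = 0.50/0.50 = 1.0, 0.76/0.24 = 3.17 and 0.98/0.02 = 49 un-enrolled people per enrolled patient. At r = 1.0, two distinct controls each cannot be found without reuse within the band; each person is used about twice on average.

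For an overall figure, two assumptions are needed: that the rates apply to the cohort, and that controls are drawn at random within band, so that D ≈ 1 + k/r. Band width × enrolment rate gives 0.5 × 0.50 = 0.25, 4.5 × 0.24 = 1.08 and 15 × 0.02 = 0.30, that is, shares of 15%, 66% and 18%.

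- 1:1: 0.153 × 2.00 + 0.663 × 1.32 + 0.184 × 1.02 = **1.37**; power 91.5%, type I error 7.2% if reuse is ignored.
- 2:1: 0.153 × 3.00 + 0.663 × 1.63 + 0.184 × 1.04 = **1.73**; power 96.3%, type I error 7.9% if reuse is ignored.

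Closest-match selection could concentrate reuse more than random draws. If distinct people filled half the control slots, with uses distributed as 1 + Poisson(1), then D = 5/2 = 2.5.

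**4. The second control.** Suppose both controls are one person, one month apart. Under a gamma-Poisson model with mean 0.6 and variance 1.96, the between-person part is 1.96 − 0.6 = 1.36 and the shared Poisson part is 0.6 × 11/12 = 0.55. The correlation is (1.36 + 0.55)/1.96 = 0.97. The 12,720 control observations are then worth 12,720/1.974 = 6,442 independent ones, and power is 95.3%. One control per patient gives 95.2%, and two independent controls 98.7%.

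**The case against.** **The protocol does not say that the regression ignores reuse.** A reader might infer from the named models that every observation is analysed as an independent patient. The documents do not support that. The model families are provisional, and matching weights or a clustered or bootstrap variance may sit in a statistical analysis plan that is not shown. This objection stands: the type I error figures are conditional on default standard errors. It does not reach the patient counts or the precision argument, which the protocol itself states.

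**There is headroom.** A reader might conclude that the study is underpowered. In the same-person case, power does fall to 80% at a total of 11,445, but that is the minimum requirement, not the planned size. At 6,360 enrolled, every 2:1 scenario above keeps at least 90%; only the 1:1 fallback drops below, once D exceeds about 1.5. This stands for power. It gives no protection on type I error, which depends on D and the matching ratio and not on the number enrolled.

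**The same-person pair is a possibility, not a forecast.** The Sample size calculation section speaks of two control patients per enrolled patient, which suggests different people. But the Control group section speaks of observations, and no rule excludes the pair.

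**The extent of reuse is unknown.** Neither the cohort's band mix nor actual reuse is given, so every D is a scenario. The direction is not in doubt.

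**Conclusion.** The point holds as an inconsistency within the protocol. The totals of 12,720 and 19,080 are counts of control observations plus enrolled patients, yet they are compared with requirements that assume independent people, and the matching rules do not provide that independence. The gain claimed for a second control shrinks to almost nothing if it is the same person one month apart.

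The consequence for inference is conditional on the variance method. If reuse were ignored, type I error would be moderately inflated at the design effects suggested by the protocol's own enrolment rates, and more so under heavier reuse.

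A loss of power below 90% is not established. The margin is, however, only as good as the 6,360. That figure is described as a minimum, but it is the change in total enrolment. If the 85% cohort share has still to be applied (assumption), 0.85 × 6,360 = 5,406 remain and the limits on D fall to about 1.13 (1:1) and 2.25 (2:1). The restriction of the data to two of the three CCGs, in the Data specification footnote, could reduce it further.

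**What to change.** - **Sample size calculation:** restate 12,720 and 19,080 as observations. Give power on the effective number of distinct control people over a range of design effects, for example 1 to 3.
- **Control group:** require the two controls of one enrolled patient to be different people.
- **Statistical method (or the statistical analysis plan):** fit the outcome models with matching weights and a variance clustered on the control person. The pseudonymised NHS number described under Data specification allows this.
- **Reporting:** give the number of distinct controls and the maximum reuse of any one person.

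The cost is some wording and a few lines of code. In return, intervals will be somewhat wider but correct, the stated power less favourable, and some second matches slightly less close.

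Exact matching on calendar month should not be required for this purpose. It would leave each enrolled patient only one record per potential control, narrowing the pool that the twelve index dates are meant to widen, and the steps above meet the concern without it.

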The subgroup analysis will be performed using interaction tests, and interpreted using credibility criteria (Sun et al. 2012). To determine whether subgroups were differentially affected by the intervention, we will compare confidence intervals from the interaction tests with the estimated effect from the pooled analysis.

Secondary analysis will also include the evaluation of health care utilisation for patients at the end of life, and evaluation of the whole cohort but accounting for attrition due to patients leaving the programme, dying, or moving out of the WELC area. Attrition will be dealt with using appropriate statistical methods, effectively using a 'person-years' denominator (this can be operationalised by using an offset term in the Poisson regression).

Sensitivity analysis for unobserved confounding

One of the main threats to the validity of this study is unobserved confounding. That is, although we anticipate that the intervention and matched control groups will be similar in terms of observed variables (such as age and prior number of hospital admissions), there may be differences between these groups that we do not observe (such as social isolation). Our findings might be biased if, for example, the patients recruited into the integrated care pathway were disproportionately isolated, and these patients were expected to have worse outcomes than other patients. We note that such selection effects would need to occur beyond the formal eligibility criteria for the integrated care programme, because the formal criteria should be exactly reproducible using the routine data (predictive risk score). However, health care professionals might have had a tendency to enrol patients with some characteristics more than others, and likewise some patients might have been more or less willing to consent to be enrolled than others.

Although there is no definitive way to assess the effect of unobserved confounding, we can compare the mortality rates of the integrated care and matched control groups (West & Thoemmes 2010). On the assumption that the integrated care pathway is unlikely to have had a large positive or negative impact on

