We will require all data sets to be pseudonymised before transfer; no patient identifiable information (*e.g.*, name, address, full date of birth) are required to complete the analysis. Pseudonymising NHS number (*i.e.*, apply a one-way hash algorithm to the NHS number, only known to the data controller) allows the data to be updated and extended, if necessary. The data sets will need to include line-level data for the top twenty per cent of patients at risk of emergency hospital admission aged over fifty years in the WELC area¹, spanning the period 1 January 2011 to 31 December 2015. Both age and risk-score vary over time, so the exact definition of these extracts will be defined in the detailed specification. We will need Read-coded GP data on registrations with GPs, prescriptions, diagnoses, and encounters, together with line-level data from the admitted patient care, outpatient and accident and emergency commissioning data sets. It would greatly assist us if some derived variables were available for the analysis (for example, the Combined Model score and constituent variables) – this would also help us standardise our variable definitions with those used locally.

¹ Note that only data from Tower Hamlets CCG and Newham CCG is to be included.

References

- Austin, P.C., 2009. Balance diagnostics for comparing the distribution of baseline covariates between treatment groups in propensity-score matched samples. *Statistics in Medicine*, 28, pp.3083–3107.
- Kaplan, E.L. & Meier, P., 1958. Nonparametric estimation from incomplete observations. *Journal of the American Statistical Association*, 53(282), pp.457–481.
- Normand, S.-L.T. et al., 2001. Validating recommendations for coronary angiography following acute myocardial infarction in the elderly: a matched analysis using propensity scores. *Journal of Clinical Epidemiology*, 54(4), pp.387–398. Available at: <http://www.ncbi.nlm.nih.gov/pubmed/11297888>.
- Roland, M. et al., 2005. Follow up of people aged 65 and over with a history of emergency admissions: analysis of routine admission data. *BMJ*, 330, pp.289–292. Available at: <http://www.bmj.com/content/330/7486/289.short> [Accessed August 21, 2012].

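### The secondary person-years analysis can cut follow-up at leaving the programme, which only enrolled patients can do, and the main count model states no time-at-risk term for patients who move away

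*Protocol*

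**What the plan says.** **Main analysis** (Protocol, Statistical method). The effect estimates come from regression models on the matched groups, and: "We will include all patients in these analyses, even if they died or moved away from the WELC area during the 12-month follow-up period". The endpoint is a count per person: "Our primary endpoint is the number of emergency hospital admissions per patient" (Endpoints). The model is a count regression: "For our primary endpoint, number of emergency hospital admissions, use of Poisson regression seems appropriate", with negative binomial as an alternative. For bed days: "We assume that ordinary least squares (linear) regression will be used". No exposure or offset term is attached to either model.

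**Secondary analysis** (Protocol, end of the Subgroup analysis section). This is described as "evaluation of the whole cohort but accounting for attrition due to patients leaving the programme, dying, or moving out of the WELC area", handled by suitable methods, "effectively using a 'person-years' denominator (this can be operationalised by using an offset term in the Poisson regression".

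**Related text.**
- Control group: controls must stay unenrolled until follow-up ends.
- Introduction: the target is the overall effect of being enrolled, not of individual interventions.
- Intervention: time on the pathway will be shown by Kaplan-Meier curves, so leaving it is an event the study expects to date.
- Data specification: the extract covers high-risk patients "aged over fifty years in the WELC area". A footnote narrows this to Tower Hamlets and Newham. GP registration data are among the items requested.

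**The concern.** There are two separate problems with time at risk.

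1. **One-sided truncation.** A person-years denominator that accounts for leaving the programme stops an enrolled patient's clock at exit. A control has no programme to leave, and no equivalent stopping date for controls is described. If patients who leave have a different admission risk from those who stay, or if their risk changes after exit, the enrolled rate is computed over selected time and the control rate is not. The resulting ratio also describes time on the programme, whereas the stated aim concerns enrolment.

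2. **Movers in the main model.** The secondary analysis is set apart from the main one by the words about accounting for attrition, which implies that the main model does not account for it. If admissions after a move out of the area are not in the data, the months after the move add nothing to the count but are treated as a full year of follow-up. A difference between groups in how often people move would then appear as a programme effect.

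The control rule makes a difference in moving plausible, though it does not show one. Someone who moves out early can no longer enrol, so the requirement to stay unenrolled tends to keep such people in the control pool.

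**Working it through.** **The plan's own figures.** Inputs from Sample size calculation: mean 0.6 admissions per year, SD 1.4, 15% change (0.15 × 0.6 = 0.09), 90% power, two-sided 0.05. The normal approximation gives 2 × (1.960 + 1.282)² × 1.4² / 0.09² for the 1:1 total, that is 5,086 per group and 10,172 in all. The noncentral t version gives 10,174 (1:1) and 11,445 (1:2), exactly as stated. The sample size calculation is therefore not in question.

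The Protocol gives no rate of moving or of leaving the programme. Everything below uses assumed rates, with the event at mid-year on average.

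**A. Leaving the programme, enrolled patients only.** Let a share L leave, with a pre-exit rate of 0.6 per year. Controls are assumed to have the same full-year mean as enrolled patients, so the true ratio is 1.

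*Rate changes after exit.* Example with L = 10% and a post-exit rate of 1.2:
- full-year mean: 0.9 × 0.6 + 0.1 × (0.3 + 0.6) = 0.630
- truncated estimate: (0.9 × 0.6 + 0.1 × 0.3) / (0.9 + 0.05) = 0.57 / 0.95 = 0.600
- apparent ratio: 0.600 / 0.630 = 0.952

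| L | Post-exit rate | Full-year mean | Apparent ratio |
|---|---|---|---|
| 10% | 1.2 | 0.630 | 0.952 (−4.8%) |
| 10% | 0.3 | 0.585 | 1.026 (+2.6%) |
| 20% | 1.2 | 0.660 | 0.909 (−9.1%) |
| 20% | 0.3 | 0.570 | 1.053 (+5.3%) |

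*Leavers differ throughout.* If leavers' rate is k times that of stayers all year, the apparent ratio is [(1 − L) + Lk/2] / {[(1 − L) + Lk] × (1 − L/2)}.
- L = 10%, k = 2: 1.00 / (1.10 × 0.95) = 0.957
- L = 20%, k = 3: 1.10 / (1.40 × 0.90) = 0.873
- L = 20%, k = 0.5: 0.85 / (0.90 × 0.90) = 1.049
- k = 1: exactly 1.000 for any L

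The most extreme case examined, L = 20% with the rate tripling after exit, gives 1 / (0.8 + 0.2 × 2) = 0.833.

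**B. Moving away, main model without offset.** Assume no admissions are recorded after a move. With m_e of enrolled patients and m_c of controls moving, the true ratio is multiplied by (1 − m_e/2) / (1 − m_c/2).

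| Enrolled move | Controls move | Multiplier |
|---|---|---|
| 5% | 5% | 1.000 |
| 3% | 8% | 0.985 / 0.960 = 1.026 |
| 3% | 10% | 0.985 / 0.950 = 1.037 |
| 5% | 10% | 0.975 / 0.950 = 1.026 |
| 5% | 15% | 0.975 / 0.925 = 1.054 |
| 10% | 5% | 0.950 / 0.975 = 0.974 |
| 15% | 5% | 0.925 / 0.975 = 0.949 |

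Under a true ratio of 0.85 and 5% against 15% moving, the observed ratio is 0.896 and the absolute difference shrinks from 0.0900 to 0.0578. With 6,360 per group the standard error is 1.4 × √(2/6,360) = 0.0248. Power falls from 95% (0.0900/0.0248 = 3.63) to 64% (0.0578/0.0248 = 2.33).

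Equal moving leaves the ratio unchanged but reduces the absolute difference slightly: 0.0900 becomes 0.0877 at 5% and 0.0855 at 10%.

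**The case against.** The strongest reply is that much of this is inferred, and several stronger readings do go too far.

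- *The main model scores movers as zero after they leave.* A reader might infer this, but the Protocol says only who is analysed. It does not say that post-move admissions go unrecorded. It leaves the exact extract definition to a later specification and keeps a hashed identifier so that data can be extended. Missing admissions are an assumption, though a likely one for an area-based extract.
- *The comparison by enrolment has been abandoned.* It has not. The main analysis does not drop time after programme exit, so enrolled patients are followed there whatever their pathway status. The departure is confined to the secondary analysis.
- *Both analyses are biased, so neither can support the other.* The text does not establish this. Exit related to health is possible but nowhere documented, and exit unrelated to admission risk causes no bias in the person-years rate. Equal moving causes none in the primary ratio.
- *The plan censors at exit.* It never uses that word. It refers to appropriate methods, and controls might be truncated at their matched patient's exit date. That detail could sit in an analysis plan not shown here.

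It is also fair to say that death and moving out are already covered by a planned person-years analysis, and that a per-patient count including deaths is a defensible estimand.

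What remains is this. The wording places an event that only enrolled patients can have in the same denominator as two that both groups can have, and says nothing to balance it. The contrast between the main and secondary analyses implies no time-at-risk term in the former.

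**Conclusion.** The point holds in a limited form. As written, the secondary person-years analysis allows follow-up to be cut in the enrolled group alone, and it then no longer estimates the overall effect of enrolment. Under the assumed conditions (5% to 20% leaving, with a rate 1.5 to 3 times higher throughout or after exit) a null effect would appear as a reduction of about 1% to 17%. If leavers' rate is half that of stayers throughout, it would appear as an increase of about 1% to 5%. The upper end of the first range is comparable with the 15% target.

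The mover point is smaller and conditional. It needs both unrecorded post-move admissions and unequal moving. Gaps of 5 to 10 percentage points then shift the primary ratio by about 2.6% to 5.4%, in either direction. Neither the direction nor the actual size of either bias can be determined from the Protocol.

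**What to change.** **Secondary person-years analysis.** Delete leaving the programme from the attrition reasons, so that enrolled patients are followed whatever their pathway status. If an on-programme analysis is wanted, make it separate, label it as such, and truncate each control observation at its matched patient's exit date. Because matching is with replacement, this has to be done per matched observation.

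**Main count model.** Add an offset for the log of time observable in the data, defined identically in both groups as time registered with a practice in the CCGs actually extracted (Tower Hamlets and Newham). Registration anywhere in WELC would be too wide: a patient moving to a Waltham Forest practice would count as observed while lying outside the extract.

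**Bed days.** Analyse on the same time basis, since an offset in the count model does nothing for the linear model.

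**Reporting.** Keep the no-offset, per-patient model as a sensitivity analysis, and report moving and death rates by group.

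**Cost.** Protocol wording and some programming; registration data are already requested. The primary effect becomes a rate per observed person-time instead of a count per patient. The offset also relies on a mover's observed time being a fair guide to the time lost. Whether time stops at death is a separate choice, and the Protocol itself treats differential mortality as a possible warning about the matching. The choice should be stated and both versions shown.

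### The protocol's own mean and SD show that the primary count is overdispersed, so an overdispersion-robust, patient-clustered model should be the default rather than a provisional Poisson

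*Protocol*

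**What the plan says.** The primary endpoint is the number of emergency hospital admissions per patient. Three places in the protocol bear on how it is modelled.

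- **Methods, Statistical method.** The protocol states that "use of Poisson regression seems appropriate" for this endpoint. The same sentence goes on to allow alternatives, with negative binomial as the example, depending on how the endpoint turns out to be distributed. The paragraph adds that suitability will be tested when the line-level data arrive. The models adjust for baseline differences that remain after matching.
- **Methods, Sample size calculation.** The assumed yearly number of emergency admissions per patient is "0.6 with a standard deviation of 1.4", taken from a previous study in a similar population. The calculation was "performed in SAS with 90% power and a two-sided p-value of 0.05" for a 15% change.
- **Methods, Subgroup analysis.** The person-years analysis for attrition names the same model: "this can be operationalised by using an offset term in the Poisson regression".

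The Control group and Statistical method sections also matter. Each potential control may supply up to 12 monthly index dates, and matching is with replacement.

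**The concern.** Poisson regression with its usual standard errors takes the variance to equal the mean. The figures used to size the study say otherwise, by a wide margin, for the same endpoint. The first-named model therefore conflicts with information that the authors already hold.

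Two things are at stake. First, if Poisson survived the promised check and was used with model-based standard errors, the intervals for the primary effect would be too narrow, and chance differences would be reported as benefit or harm too often. Second, the choice of primary model is left until outcome data are in hand, with no rule for making it. The fact that would settle the choice is already in the protocol, so this analyst decision is avoidable.

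A separate source of understated error is not cured by changing the distribution. The same control patient can enter the analysis several times, under different index dates or as the match for several enrolled patients. The outcomes of those records overlap or are identical.

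**Working it through.** **Inputs.** All are from the Sample size calculation section: mean 0.6, SD 1.4, a 15% change (0.15 × 0.6 = 0.09 admissions per patient-year), 90% power, two-sided 0.05, and at least 6,360 enrolled patients.

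**1. Reproduce the protocol's sample size.** Comparing two means by the normal approximation, with (1.960 + 1.2816)² = 10.507:

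- One control each: n per group = 2 × 10.507 × 1.4² / 0.09² = 5,086 after rounding up, total 10,172. The protocol states 10,174.
- Two controls each: n enrolled = 1.5 × 10.507 × 1.4² / 0.09² = 3,814 after rounding up, total 11,442. The protocol states 11,445.

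Both agree to within rounding or a t correction, so the SD of 1.4 is the operative planning figure. A Poisson variance of 0.6 in the same formula gives 2 × 10.507 × 0.6 / 0.09² = 1,557 per group, total 3,114. The study was therefore sized for much more variation than Poisson allows.

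**2. Overdispersion implied by the planning figures.** Variance/mean = 1.4²/0.6 = 1.96/0.6 = 3.27. A Poisson count with mean 0.6 has SD √0.6 = 0.77, not 1.4. The true standard error is √3.27 = 1.81 times the Poisson one, so a Poisson interval has 1/1.81 = 0.55 of the correct width.

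**3. Consequence if plain Poisson is kept, no covariates.**

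- Type I error = 2 × [1 − Φ(1.96/1.81)] = 0.278. Coverage of a nominal 95% interval = 0.722. Neither depends on the number of patients.
- A simulation of negative binomial counts (mean 0.6, variance 1.96, 6,360 per group, 4,000 replicates) gave 27.2% type I error with Poisson standard errors and 4.8% with empirical-variance standard errors.
- With 6,360 per group, the standard error of the log rate ratio is √[(1.96/0.36)(2/6,360)] = 0.0414 from the planning SD, and √[(1/0.6)(2/6,360)] = 0.0229 under Poisson. The 95% half-widths are 0.081 and 0.045 on the log scale. Poisson would call a rate increase of about 4.6% significant, where the planning SD requires about 8.4%.

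**4. Allowing for covariates.** The excess variance is 1.96 − 0.6 = 1.36. If adjustment leaves a fraction f of it, the ratio is 1 + 1.36f/0.6. The documents give no value for f, so the range below is assumed.

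| Excess variance removed | Ratio | Type I error |
|---|---|---|
| 0% | 3.27 | 28% |
| 30% | 2.59 | 22% |
| 50% | 2.13 | 18% |
| 70% | 1.68 | 13% |

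To bring type I error down to 10%, the ratio must fall to (1.96/1.645)² = 1.42, which means removing about 81% of the excess.

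**5. Repeated controls.** The protocol gives no expected reuse rate, so this effect cannot be sized. Its direction is clear: treating repeated records of one patient as independent understates the standard error, whichever count distribution is fitted.

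**The case against.** The strongest reply is that the protocol does not commit to Poisson. The sentence that calls it appropriate also names negative binomial as an alternative, and the paragraph promises a check of suitability. With dispersion near 3.3 and more than 12,000 patients, a reasonable check would detect the problem. Narrow intervals follow only if the check fails or is ignored, Poisson is kept, and unscaled model-based errors are used. The protocol does not say which type of standard error is meant, and that detail may sit in a statistical analysis plan that is not shown. The ratio of 3.27 is also unadjusted and comes from an earlier study. The planned covariates, which include risk score and prior utilisation, should explain some of the variation. The person-years remark is only an example within a secondary analysis, and an offset works equally well in a negative binomial model.

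Most of this stands. A reader might infer that the primary confidence intervals will be far too narrow, or that 28% is the expected error rate. The protocol does not support either: the first is conditional, and the second is an upper figure for an unadjusted analysis. A reader might also infer that the overdispersion leaves the study underpowered. It does not, because the calculation already uses the SD of 1.4.

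The reply does not justify waiting. The evidence for overdispersion is already in the protocol, the switch has no criterion, and it would be made with outcomes visible. The clause on alternative distributions also does nothing about repeated control patients.

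**Conclusion.** The point holds as one that should be fixed, not as a fatal flaw. On the protocol's own planning figures the variance is 3.27 times the mean, so Poisson is not a suitable first choice for the primary endpoint, even provisionally. If it were retained with model-based errors, type I error could reach about 28% and coverage could fall to about 72% without adjustment. With adjustment the inflation would be smaller by an unknown amount, and 13% to 22% if covariates removed 70% to 30% of the excess variance.

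These figures assume that the earlier study's mean and SD carry over to this cohort and that records are independent. Reuse of controls would make matters worse to an extent that the documents do not allow one to calculate. The finding rests on the conflict between two statements in the protocol, not on detail that a protocol may properly leave to an analysis plan.

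**What to change.** In the Statistical method section, name negative binomial regression (or quasi-Poisson, a log-linear model whose variance is not tied to the mean) as the default for emergency admissions. Fix this before outcomes are examined, with robust standard errors clustered on pseudonymised patient ID. The Data specification already provides for a pseudonymised NHS number, so the identifier should be available. In the Subgroup analysis section, replace the reference to Poisson with the same model plus the person-years offset. Checks of distribution can stay as diagnostics, but should not decide the primary model.

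The change takes about one sentence in each place and a standard software option, and needs no new data. Intervals will be wider than under plain Poisson, and correct. Allowing for the overdispersion costs no planned power: taking the protocol's 6,360 per group at face value and treating all records as independent, power at SD 1.4 is Φ[0.09/(1.4 × √(2/6,360)) − 1.96] = Φ(1.665), about 95%. Control reuse would reduce this by an amount that is known only after matching.
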